### **6.3. Pre-Screening**

A trained study staff member will pre-screen interested veterans and active-duty service members for basic eligibility requirements (see above for inclusion criteria and exclusion criteria) and schedule consent and eligibility/baseline assessment appointments with site RA. (See Phone Screen submitted with this protocol for details.)

**Based on the answers to this phone screen questionnaire, this subject:**

**1. Subject does not qualify.**

- a. Subject will be thanked for their time and the phone call terminated.
  - b. If the subject did not qualify due to recent suicidal ideation, if deemed necessary by the PI (a licensed Neurologist), a licensed Behavioral Health Provider will be contacted to provide appropriate follow up care.
  - c. Subject will be informed of other options for care. These options are on the Handout “Post-Study Resources for Participants”. Handouts may be read to veteran and active-duty service members over the phone and/or mailed to the veteran and active-duty service member if requested.
- 2. Subjects who do not clearly fail, or meet, the study criteria** will be told that the rest of the study team will need to be contacted to determine if the subjects are eligible or not. Subject will then be contacted to be told the team’s decision.
- 3. Veterans and active-duty service members who pass the phone screening** will be asked to come in for an enrollment visit.

**6.4. Enrollment: Visit 1, Day 0**

Those who pass the telephone pre-screening will be scheduled for an Enrollment Visit (Visit 1, Day 0).

Procedures to be done at this visit include:

1. Re-check of inclusion/exclusion criteria prior to signing enrollment forms.
2. Signing of Informed Consent Form (ICF) and HIPAA
3. Completion of a Demographics Form
4. Baseline Psychometric Instruments:
  - a. Pittsburgh Sleep Quality Index (PSQI)
  - b. PSQI Addendum for PTSD (PSQI-A)
  - c. PCL-5 Checklist (past 1 month)
  - d. Clinician-Administered PTSD Scale for DSM-5 (CAPS-5)
  - e. Patient Health Questionnaire-9 past 1-month version (PHQ-9) (Score greater than or equal to 20 indicates severity of depression too great for this study. Score of 1 or more on the suicide ideation item [question #9] to trigger a risk assessment by PI and a licensed Behavioral Health Provider.)
  - f. Epworth Sleepiness Scale ESS: On question #8 any score above “0” will prompt an additional question:
    1. Do you drive (“get behind the wheel”) when you are drowsy?
      - a. Answer must be “No” to be enrolled in the study due to safety concerns.
  - g. DAST-10: Exclude if score is greater than two (2).
  - h. AUDIT: Exclude if score is equal to, or greater than, eight (8).
  - i. Functional Outcomes of Sleep Questionnaire (FOSQ)
  - j. Insomnia Severity index (ISI)
  - k. Trauma Related Nightmare Scale (TRNS)

- l. VR-12 Quality of Life (VR-12)
- m. NW Likert Scale for Sleep Quality (NW Likert) 7-day
- n. Columbia-Suicidality Severity Rating Scale, Lifetime and Recent version (C-SSRS) (responses in the High-Risk range will make the subject ineligible).
  - i. After further assessment with the PI, Study Staff will contact the healthcare provider that has been trained to perform a suicide assessment for all subjects with a rating greater than “LOW”.
- o. RedCAP collection questionnaire: What type or types of traumas led to your PTSD? (Choose the primary type of trauma that applies) 1) Combat/blast trauma 2) Sexual Trauma/Rape/Sexual Assault 3) Natural Disaster 4) Childhood physical abuse 5) Accident, such as a car accident 6) Other (a secondary choice would appear for free text).
5. Baseline health assessments
  - a. Blood Pressure-Blood pressures should be taken while the patient is in a sitting position with their feet flat on the ground after at least 5 minutes of rest. A minimum of 2 blood pressures should be taken 30-60 seconds apart. The average of these two blood pressures should be recorded.
  - b. Height and Weight to calculate BMI
  - c. Complete a Health Questionnaire
  - d. Medication Reconciliation (compare to EHR, add any over the counter medications)
6. Determination of subject’s eligibility for randomization:
  - a. Based on each subject’s scores and answers to the previous questionnaires/questions the subject will either be:
    - i. Randomized.
      1. The enrollment visit will continue.
    - ii. Told that he/she does not qualify.
      1. Enrollment visit ends.
      2. Subjects are reimbursed for their time/assessments.
      3. Subject given contact information for behavioral health services.
      4. No further contacts/visits will be scheduled.
7. Randomization.
  - a. Eligible subjects with scores equal to or more than 16 (PSQI High stratum), will be randomized separately from subjects whose scores were equal to a minimum of 10 to a maximum of 15 (PSQI Low stratum).
    - i. Both the 16 and over scoring group and the 15 and under scoring group will have 50% of their group given the Active System and 50% will get the Sham System.
  - b. PSQI Low stratum subjects will have assigned ID #'s ending in 001 to 499.
  - c. PSQI High stratum subjects will have ID #'s ending in 500 to 999.
8. NW System provided to subject
  - a. Systems will be pre-prepared by NW Corporate.
  - b. Pre-prepared Systems will be labeled with the study ID number used.
  - c. Subjects will then be randomized using the randomization procedure delineated in section 6.1.
  - d. Once the subject is randomized, the system will be set to sham or active mode by NW technical staff.
    - i. These staff are not located at the study site.
    - ii. Neither the subject nor the study staff will have access until data is unblinded.
9. Subject training on NW System:
  - a. Subjects will be instructed on the proper use and care of the phone and watch.
  - b. Subjects will be shown how to Access and Use the NW Application.

- c. Verify that participant understands how to use the NW System
- d. Send participant home with directions “Home Instruction Sheet”
  - i. The Contact Number for Study Staff is included in the Home Instruction Sheet, so if there is/are any issue(s) prior to the Checkup Call the subject may obtain help solving the issue(s)
10. Complete the NW Call and Visit Schedule (included in this submission).
  - a. Subjects will fill-in their own copy of the form and take it home with them.
11. Stress to subject that ANY ISSUES with the phone and/or watch must be reported promptly to Study Staff so that they can be corrected.
12. Inform subjects that Study Staff may call DAILY from days 2-6 (optional—dependent on subject understanding, connectivity issues, etc.). These calls have been named “Help Calls”.
13. Enrollment status and subject ID will be placed into a spreadsheet that indicates Study ID #, name, last 4, contact phone, address, and the serial number of the pre-prepped System that was provided to the subject.
  - a. This spreadsheet will NOT be shared with NightWare personnel as it contains PHI.
14. A second spreadsheet will keep track of all pre-prepared phones and watches received from NW.
  - a. Phone and watch passcodes as well as the NW Application log-in key code will be tracked upon receipt.

### **6.5. Calibration of System (Days 0-3, approximately)**

Once the NW Active System has been installed on the watches of those participants randomized to receive study intervention, a calibration period consisting of the recording of approximately 500 minutes of normal (non-intervention) sleep will occur. This calibration allows for a Stress Index (Threshold) to be assigned for the participant. Sham Systems will not go through a calibration phase, nor will they ever provide study interventions.

### **6.6. Treatment Operation (Study Intervention, Post-Calibration, Daily Use Questionnaire )**

After the calibration period, the Active System enters active treatment (study intervention) on approximately days 2-3. The Sham System will never go into this mode. Subjects will also receive a daily use questionnaire Deployed via RedCAP

1. RedCAP deployed Daily Use questionnaire (Day 1-90)
  - a. How was your sleep quality? 0 = Refreshing, 1 = Average, 2 = Poor
  - b. Was the device disruptive? 0 = Did not feel it, 1 = Mildly disruptive, 2 = Uncomfortable
  - c. How many nightmare-related awakenings? 0 = none, 1 = 1-2, 2 = 3 or more

### **6.7. Day 1: Startup Phone Call**

This call will be to see if subjects have gotten the NW System connected to their home WiFi and were able to set things up and use the system during the night

Administer:

1. NW Start up Call Questionnaire.

Any issues that arise will be dealt with by Study Staff (help with calling participant’s internet service provider to get the System synced with the participant’s home WiFi, additional education on how to wear the watch and use the application, etc.).

## **6.8. Days 2-6 and others if needed: Help Calls/Texts (Optional)**

After doing the Start Up Call on Day 1, research staff will conduct additional calls/texts on days 2-6, and on other days, as needed. During these calls/texts, research staff will address any issues arising with WiFi connectivity, misunderstandings and the proper use of the devices, as well as any other issues that may arise. Administer the following questionnaire (as needed): Help Calls.

## **6.9. Day 7: Checkup Phone Call**

Study staff will call on Day 7 (+/- 2 days) to determine how the participant is doing with the NW System. Administer:

- a. NW Help Calls Questionnaire

## **6.10. Day 14: Patient Questionnaire Assessment**

Participants will complete questionnaires on Day 14 (+7 days). Study coordinator will contact participants on Day 16 if the questionnaires have not yet been completed. Questionnaires to be completed:

- a. Administer the PCL-5.
- b. Administer the PHQ-9
- c. Pittsburgh Sleep Quality Index (PSQI)

## **6.11. Day 21: Checkup Phone Call**

Study staff will call on Day 21 (+7 days) to determine how the participant is doing with the NW System. Administer:

- a. NW Help Calls Questionnaire

## **6.12. Day 30: Visit 2 - In person follow up**

The following events/assessments will occur at the in-person 30-day (+ 7 days) visit.

Health assessments

### **2. Psychometric Instruments:**

- a. Pittsburgh Sleep Quality Index (PSQI)
- b. PSQI Addendum for PTSD (PSQI-A)
- c. PCL-5
- d. Insomnia Severity Index (ISI)
- e. (PHQ-9) (Score of 1 or more on the suicide ideation item [question #9] to trigger a risk assessment by a licensed Behavioral Health Provider if deemed necessary by the PI.)
- f. Epworth Sleepiness Scale ESS
- g. Functional Outcomes of Sleep Questionnaire (FOSQ)
- h. Trauma Related Nightmare Scale (TRNS)
- i. VR-12 Quality of Life (VR-12)
- j. NW Likert Scale for Sleep Quality (NW Likert)
- k. Columbia-Suicidality Severity Rating Scale, Since Last Contact version (C-SSRS)
  - i. If deemed necessary by the PI, Study Staff will contact a healthcare provider that has been trained to perform a suicide assessment if there is any risk of suicide.
- l. Blinding Assessment Questionnaire

### **3. Health assessments**

- a. Blood Pressure- Blood pressures should be taken while the patient is in a sitting position with their feet flat on the ground after at least 5 minutes of rest. A minimum of 2 blood pressures should be taken 30-60 seconds apart. The average of these two blood pressures should be recorded.
- b. Height and Weight to calculate BMI
- c. Medication Reconciliation

Every effort will be made to get the subject to the Study Site for an in-person visit. However, if the participant absolutely cannot come in, the assessments can be made by phone or mail and a deviation recorded. Blood pressure and BMI assessments will not be able to be done.

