### **6.13. Day 60: Visit 3 – Patient Questionnaire Assessment**

Participants will complete questionnaires on Day 60 (+7 days). Study coordinator will contact participants on Day 62 and after if the questionnaires have not yet been not completed.

Procedures to be done during the call: Questionnaires to be completed:

1. Psychometric Instruments:
  - a. Pittsburgh Sleep Quality Index (PSQI)
  - b. PCL-5
  - c. (PHQ-9) (Score of 1 or more on the suicide ideation item [question #9] to trigger a risk assessment by the PI, and if necessary, a licensed Behavioral Health Provider.)
  - d. Epworth Sleepiness Scale ESS
  - e. Trauma Related Nightmare Scale (TRNS)
  - f. Insomnia Severity index (ISI)
  - g. VR-12 Quality of Life (VR-12)
  - h. NW Likert Scale for Sleep Quality (NW Likert)
  - i. Columbia-Suicidality Severity Rating Scale, Since Last Contact version (C-SSRS)
    - i. Study Staff will immediately contact the PI, and if necessary, a healthcare provider that has been trained to perform a suicide assessment if there is any risk of suicide.

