#### **9.1.3. Assessment of Potential Risks and Benefits**

Study inclusion and exclusion criteria were designed to only include subjects already suffering from sleep disorder and therefore most likely to benefit from the intervention.

Since the intervention is delivered through a non-invasive smartwatch, study participants may simply discontinue wearing the watch if the intervention is contributing to deteriorating sleep quality.

The trial includes a primary safety endpoint designed to evaluate worsening sleep quality:

1. Epworth Sleepiness Scale

The trial also includes a secondary safety endpoint designed to evaluate worsening suicidal risk:

1. Columbia-Suicide Severity Rating Scale (C-SSRS LT) will be administered at the beginning and end of the study.
  - a. The Lifetime and Recent version will be used to determine if the subject is suitable for this study.
    - i. Potential Subjects that have a rating of “High” will be excluded from this study.

- ii. Since a “High” rating is an imminent safety risk, study staff will immediately call/page the PI, and if needed, a licensed staff member to conduct a safety assessment.
  1. If there isn’t a licensed staff person available, the subject will be TAKEN to the Hospital Emergency Room.
- b. At the 30, 60, and 90 day visits(+7 days), the subject will take another C-SSRS, the Since Last Contact version.
  - i. Either an increase in or a “High” score is an imminent safety risk, so study staff will immediately call/page licensed staff member to conduct a safety assessment.
    1. If there isn’t a licensed staff person available, the subject will be TAKEN to the Hospital Emergency Room.

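### The Day 30 fallback lets the suicide-risk screens be mailed with no limit on when they are read, and section 6.12 does not carry over the immediate response required by section 9.1.3

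*Protocol*

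**What the plan says.** Protocol section 6.12 lists the C-SSRS (Since Last Contact version, item k) and the PHQ-9 (item e) among the Day 30 instruments. The visit is meant to be in person. Failing that, "if the participant absolutely cannot come in, the assessments can be made by phone or mail and a deviation recorded". The next sentence names what is then lost: "Blood pressure and BMI assessments will not be able to be done".

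The response to a positive C-SSRS appears in two places.

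- Section 6.12, item k.i: "If deemed necessary by the PI, Study Staff will contact a healthcare provider that has been trained to perform a suicide assessment", which applies "if there is any risk of suicide".
- Section 9.1.3 says that at the 30, 60 and 90 day visits "the subject will take another C-SSRS, the Since Last Contact version". An increase, or a High "score is an imminent safety risk, so study staff will immediately call/page licensed staff member to conduct a safety assessment". If no licensed person is available, "the subject will be TAKEN to the Hospital Emergency Room".

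For comparison, the Day 60 instruction in section 6.13 reads "Study Staff will immediately contact the PI, and if necessary, a healthcare provider that has been trained to perform a suicide assessment", and section 6.14 words Day 90 in the same way. The SAP describes the C-SSRS hypothesis but says nothing about remote administration or review of forms.

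**The concern.** An immediate response rule works only if staff learn the answer promptly. A participant who completes a C-SSRS on paper at home and posts it may have reported something the protocol itself regards as an imminent risk, and nobody at the site knows until the envelope is opened and the form read. The same holds for PHQ-9 item 9, where section 6.12 has a score of 1 or more lead to a risk assessment if the PI thinks it necessary.

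Day 30 is the only C-SSRS after baseline in the 30-day randomized period (sections 1.1 and 1.3). Change in C-SSRS to Day 30 is also a safety outcome, listed as primary in the synopsis and as secondary in section 7.5. The main stake is participant safety, not inference.

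A second weakness lies in the wording of item k.i. Its trigger is broad enough to include increased and High ratings, yet it sets no time and depends on the PI's judgement. Staff working from the visit section alone could miss the stricter rule in section 9.1.3.

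**Working it through.** No formula applies, so the check is to set the texts side by side.

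**Step 1. Does the mail option reach the C-SSRS?** The sentence stands under the Health assessments item of section 6.12, so it might be thought to cover only that item. But that item consists of blood pressure, height and weight for BMI, and medication reconciliation, and the text says blood pressure and BMI cannot be done remotely. Read that narrowly, the fallback would cover medication reconciliation alone. It also speaks of the visit as a whole. The sensible reading is that it covers the psychometric instruments too. Nothing exempts the C-SSRS or PHQ-9, and nothing prefers phone to mail for them.

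**Step 2. Does any time limit cover a posted form?** The delay is time in the post plus time until staff read the form.

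| Possible limit | What it governs |
|---|---|
| Day 30 window (+7 days in 6.12; +/-7 in 1.3) | When the visit takes place |
| Deviation reporting (section 11: 10 working days from identification, or 3 from the scheduled activity if found at once) | Reporting the deviation |
| Paper forms (section 13.1) | Locked storage until data entry, with no deadline |
| Immediate call or page (9.1.3) | Action once the score is known |

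None limits either part of the delay. The documents give no postal time, no reading time and no expected number of mail users, so neither the delay nor the number affected can be computed.

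**Step 3. Compare the response rules.**

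| Source | Days | Timed? | Conditional? |
|---|---|---|---|
| 6.12, item k.i | 30 | No | Yes, on the PI |
| 6.13 and 6.14 | 60 and 90 | Immediate contact with the PI | Only the further referral |
| 9.1.3 | 30, 60 and 90 | Immediate | No, for an increase or High |

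Of the three post-baseline C-SSRS visits, two have an immediate instruction in their own section. Day 30 does not, although section 9.1.3 covers it.

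**Step 4. Can the emergency step be carried out remotely?** Taking the participant to the emergency room presumes that the participant is with staff. No equivalent is given for someone at home. This affects any remote C-SSRS, by phone or by mail, at Days 30, 60 and 90.

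**What not to use as the size.** The Day 30 C-SSRS falls 30 - 0 = 30 days after the previous one, and 30 - 14 = 16 days after the last scheduled PHQ-9, before windows. These are features of the visit schedule and are the same for people who attend in person. They do not measure the mail delay.

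**The case against.** The strongest reply is that any remotely completed form must be read before anyone can act, that section 9.1.3 applies whatever the mode, and that mail is a last resort after every effort at an in-person visit, recorded each time as a deviation. Phone is offered in the same sentence. Section 13.1 describes electronic completion on the study phone, section 5.2 excludes High C-SSRS risk at entry, the PHQ-9 is repeated at Day 14, there is a Day 21 call, participants hold a staff number, and people who stop wearing the device are contacted.

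Most of this stands, and it is why the point is minor. It does not close the gap. The entry exclusion describes Day 0. Section 6.10 lists the Day 14 PHQ-9 without an item 9 instruction. The Day 21 call and the contact about device use concern the system and list no suicide screen. Section 6.12 does not require electronic completion in place of mail. Recording a deviation does not get the form read sooner.

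Two further objections stand. First, Days 60 and 90 are routinely completed as remote questionnaires, also with no stated review time, so Day 30 is not uniquely weak there. Second, banning mail outright could turn a late screen into no screen for someone who cannot be reached by phone. The fix allows for that.

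A reader might infer that sections 6.12 and 9.1.3 contradict each other. The documents do not support this: item k.i can be read as a layer below section 9.1.3, which names the 30-day visit and still applies. Operational detail may also sit in study documents submitted separately and not available here.

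**Conclusion.** The point holds as a minor safety gap with a cheap improvement. In a rarely used fallback, the Day 30 C-SSRS and PHQ-9 may be mailed with no limit on when they are read, and the response in section 9.1.3 waits until they are. Independently of mail, item k.i states a weaker Day 30 rule than section 9.1.3 and does not refer to it. The missing off-site emergency step is a related gap but not specific to mail.

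The size cannot be given. That few participants are affected is a judgement based on the last-resort wording, not a figure in the documents. A reader might also infer that at-risk participants would go unnoticed for weeks; nothing in the documents establishes a delay of any particular length. The conclusion assumes that the mail sentence covers the psychometric instruments and that no separate site procedure already sets a review time.

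**What to change.** **Section 6.12, fallback.** When a participant cannot attend, staff give the C-SSRS and PHQ-9 item 9 on the phone call already allowed. Mail is used for these two only if documented phone attempts fail, and any mailed form is reviewed on the day of receipt. The other questionnaires may still be mailed.

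**Section 6.12, item k.i.** State that an increased or High rating triggers the immediate response in section 9.1.3, and keep the PI's judgement for lesser risk.

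**Section 9.1.3.** Add an off-site equivalent of the emergency-room step: confirm the participant's location at the start of the call and, if no licensed person is available, send emergency services there. This would cover any remote C-SSRS at Days 30, 60 and 90. Sites already hold phone numbers and addresses (section 6.4, item 13).

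**Cost.** A few sentences, and short calls to the few who miss the Day 30 visit. No new instrument or visit is needed. Same-day review shortens the wait after a mailed form arrives but cannot remove time in the post. The change does not set a review time for the routine remote questionnaires at Days 60 and 90.

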### **6.13. Day 60: Visit 3 – Patient Questionnaire Assessment**

Participants will complete questionnaires on Day 60 (+7 days). Study coordinator will contact participants on Day 62 and after if the questionnaires have not yet been not completed.

Procedures to be done during the call: Questionnaires to be completed:

1. Psychometric Instruments:
  - a. Pittsburgh Sleep Quality Index (PSQI)
  - b. PCL-5
  - c. (PHQ-9) (Score of 1 or more on the suicide ideation item [question #9] to trigger a risk assessment by the PI, and if necessary, a licensed Behavioral Health Provider.)
  - d. Epworth Sleepiness Scale ESS
  - e. Trauma Related Nightmare Scale (TRNS)
  - f. Insomnia Severity index (ISI)
  - g. VR-12 Quality of Life (VR-12)
  - h. NW Likert Scale for Sleep Quality (NW Likert)
  - i. Columbia-Suicidality Severity Rating Scale, Since Last Contact version (C-SSRS)
    - i. Study Staff will immediately contact the PI, and if necessary, a healthcare provider that has been trained to perform a suicide assessment if there is any risk of suicide.

